4.6 Determination of the Sample Size

1) Number of Subjects to be Recruited

Taking into account the 20% withdrawal rate, this clinical study plans to enroll a total of 519 subjects (173 per group).

Protocol No.: DW_UDCA005 English Translation Version

2) Calculation Basis

The primary objective of this study is to assess the efficacy of the study drug compared with placebo in preventing gallstone formation after gastrectomy in patients with gastric cancer. If the efficacy of DWJ1319 300 mg or 600 mg versus placebo is statistically significant, the study drug is considered to demonstrate its superiority. The endpoint is the percentage of subjects forming gallstones within 12 months of gastrectomy. The hypothesis to test this is as follows:

 H_0 (Null hypothesis): $P_{T1} = P_C$ and $P_{T2} = P_C$ H_1 (Alternative hypothesis): $P_{T1} \neq P_C$ or $P_{T2} \neq P_C$

P_{T1}: Proportion of subjects forming gallstones after taking 600 mg of DWJ1319

P_{T2}: Proportion of subjects forming gallstones after taking 300 mg of DWJ1319

P_C: Proportion of subjects forming gallstones after taking placebo

For testing of each treatment group versus the placebo, the significance level of the test is not corrected because a sequential multiple test (twice) is performed using the fixed sequece method. The test sequence is 600 mg of DWJ1319 versus placebo and 300 mg of DWJ1319 versus placebo.

The following results were referenced to calculate the number of subjects to be tested.

	Placebo	Ursodiol	Ursodiol	Ursodiol	
Placebo		300 mg	600 mg	1,200 mg	
Study 1 (6M)	32.14% (18/56)	13.21% (7/53)	1.64% (1/61)	6.35% (4/63)	
Study 2 (12M)	16.94% (112/661)	-	-	-	
Study 3 (12M)	13.64% (6/44)	-	-	-	

In this clinical study, the incidence of gallstones with placebo was estimated to be 18%, which is the weighted average of study 1, 2 and 3, where study 1 is the result of placebo in obese patients who underwent gastrectomy and studies 2 and 3 are the adjusted results of placebo in patients with gastric cancer who underwent gastrectomy. Since it is difficult to estimate the incidence of gallstone of DWJ1319 by each dose, 7%, which is the weighted average of the three Ursodiol treatment groups in study 1, was estimated as the rate of gallstone formation for the study drug.

In addition to the above assumptions, the significance level is 5% for two-sided test, 80% for test power, and the minimum number of subjects for 1:1:1 assignment is as follows.

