8.4.1 Primary Efficacy Analysis

The primary efficacy endpoint is the percentage of subjects with gallstone formation within 12 months of gastrectomy based on the external investigator's assessment.

For the superiority test of DWJ1319 over placebo on the incidence of gallstone formation, sequential multiple testing will be performed for each treatment group according to the fixed sequence method.

Step 1: Superiority testing for DWJ1319 600 mg compared with placebo (5% significance level)

Protocol No.: DW_UDCA005 English Translation Version

Step 2: Superiority testing for DWJ1319 300 mg compared with placebo (5% significance level)

As DWJ1319 600 mg is expected to be relatively more effective in preventing gallstones compared to DWJ1319 300 mg, the efficacy assessment of DWJ1319 600 mg versus placebo is given priority.

The step 2 test can be performed only if the result of the step 1 test is statistically significant, and conclusions about the superiority of DWJ1319 over placebo will be drawn based on the test result from each step. If the result of the step 1 test is not statistically significant, the step 2 test will not be performed, and it will be concluded that both treatment groups of DWJ1319 have failed to demonstrate superiority over placebo.

The frequency, percentage (%), and corresponding 95% confidence intervals are presented for the subjects with gallstone formation within 12 months by each treatment group. The comparison between each treatment group of DWJ1319 versus the placebo is analyzed using the Logistic Regression Model, with the lymph node resection range (D1+, D2) and the type of gastrectomy (Total gastrectomy, partial gastrectomy) as the covariates and the respective factors are defined as the following. The factors are defined as treatment group (DWJ1319 600 mg vs Placebo) for Step 1, treatment group (DWJ1319 300 mg vs Placebo) for Step 2, and treatment group (Placebo, DWJ1319 600 mg and DWJ1319 300 mg) for sensitivity analysis. Logistic Regression Model results are presented as odds ratios, corresponding 95% confidence intervals and two-sided p-values, and p-value is used for the final determination.

A summary of the data is presented in the following tables.

- T. Percentage of Subjects with Gallstone Formation within 12 month by the External Investigator's Assessment [DWJ1319 600mg vs Placebo] (FAS)

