8.4.2 Secondary Efficacy Analysis

1) Percentage of subjects forming gallstones within 3, 6, 9, and 12 months from

Protocol No.: DW UDCA005

English Translation Version

gastrectomy

- 2) Percentage of subjects forming gallstones within 3, 6, and 9 months from gastrectomy as assessed by the external investigator
- 3) Percentage of subjects forming biliary sludge within 3, 6, 9, and 12 months from gastrectomy

For the secondary endpoints 1), 2), and 3), the comparison between each treatment group of DWJ1319 versus the placebo is analyzed using the Logistic Regression Model, with the treatment groups (DWJ1319 600 mg/DWJ1319 300 mg vs Placebo) as the factor and the lymph node resection range (D1+, D2) and the type of gastrectomy (Total gastrectomy, partial gastrectomy) as the covariates. Logistic Regression Model results are presented as odds ratios, corresponding 95% confidence intervals and two-sided p-values.

4) Time to gallstone formation

For the time to gallstone formation, the median and corresponding 95% confidence intervals, and standard error values are presented. The comparison between each treatment group of DWJ1319 versus the placebo is analyzed using the Cox Proportional Hazards regression Model and the two-sided p-values are presented, with the treatment groups (DWJ1319 600 mg/DWJ1319 300 mg vs Placebo) as the factor and the lymph node resection range (D1+, D2) and the type of gastrectomy (Total gastrectomy, partial gastrectomy) as the covariates.

A summary of the data is presented in the following tables.

- T. Percentage of Subjects with Gallstone Formation within 3, 6, 9, 12 month by the Investigator's Assessment (FAS)
- T. Percentage of Subjects with Gallstone Formation within 3, 6, 9, 12 month by the Investigator's Assessment (PPS)
- T. Percentage of Subjects with Gallstone Formation within 3, 6, 9 month by the External Investigator's Assessment (FAS)
- T. Percentage of Subjects with Gallstone Formation within 3, 6, 9month by the External Investigator's Assessment (PPS)
- T. Percentage of Subjects with Biliary Sludge Formation within 3, 6, 9, 12 month by the Investigator's Assessment (FAS)
- T. Percentage of Subjects with Biliary Sludge Formation within 3, 6, 9, 12 month by the Investigator's Assessment (PPS)
- T. Time to Gallstone Formation (FAS)
- T. Time to Gallstone Formation (PPS)

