11.1 Statistical Analysis Methods

When a confidence interval for a ratio is presented, an accurate confidence interval is presented when a cell with an expected frequency of less than 5 is equal to 20% or higher of all cells. In addition, if the odds ratio is estimated to be infinite including the cell with a frequency of 0 when presenting the odds ratio, the odds ratio is estimated using Firth's Penalized Maximum Likelihood and a profile-likelihood confidence interval is presented.

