15.3 Comparison for Between Treatment Groups

ANOVA

PROC GLM DATA = dataset;

CLASS treatment;

MODEL variable = treatment;

RUN;

Kruskal-Waillis test

PROC NPAR1WAY DATA = dataset WILCOXON;

CLASS treatment;

VAR variable;

RUN;

Chi-square or Fisher's exact test

PROC FREQ DATA = dataset;

TABLE treatment * variable/CHISQ FISHER;

RUN;

ANCOVA

PROC GLM DATA = dataset;

CLASS treatment covariate (categorical);

MODEL variable = treatment covariate;

LSMEANS treatment/PDIFF CL STDERR;

ESTIMATE 'DWJ1319 600 mg or 300 mg vs Placebo' treatment 1 -1;

RUN;

Logistic regression model

PROC LOGISTIC DATA = dataset;

CLASS treatment covariate (categorical)/param=ref ref=last;

MODEL variable = treatment covariate;

Protocol No.: DW_UDCA005 English Translation Version

ESTIMATE 'DWJ1319 600 mg or 300 mg vs Placebo' treatment 1 -1 /EXP;

RUN;

Logistic regression model (in case of including cells with frequency of 0)

PROC LOGISTIC DATA = dataset;

CLASS treatment covariate (categorical)/param=ref ref=last;

MODEL variable = treatment covariate/ firth clodds=pl;

RUN;

Cox Proportional Hazards regression Model

PROC PHREG DATA = dataset;

CLASS treatment covariate (categorical)/param=ref ref=last;

MODEL time * status(censored) = treatment covariate / RL;

CONTRAST 'DWJ1319 600 mg or 300 mg vs Placebo' treatment 1 -1 / ESTIMATE =EXP;

RUN;

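### In the zero-cell case the SAP fixes a Firth odds ratio with a profile-likelihood interval but no matching treatment test, so a secondary or exploratory row can show an interval excluding 1 beside p > 0.05

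*Protocol*

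**What the plan says.** SAP 11.1, Statistical Analysis Methods (the second section with that number), covers the case where a cell with no events makes the odds ratio infinite: "the odds ratio is estimated using Firth's Penalized Maximum Likelihood and a profile-likelihood confidence interval is presented". It names an estimator and an interval, but no test.

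SAP 15.3 gives the model line for this case as "MODEL variable = treatment covariate/ firth clodds=pl". The options ask for the Firth penalty and profile-likelihood limits for the odds ratio. Unlike the ordinary logistic program printed just above it, this one has no ESTIMATE statement.

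A p-value is nevertheless needed. For the secondary proportions SAP 8.4.2 says "Logistic Regression Model results are presented as odds ratios, corresponding 95% confidence intervals and two-sided p-values", and SAP 8.4.3 asks for the same output for bile reflux on endoscopy and for AST/ALT abnormalities. SAP 8.4.1, on the 12-month primary endpoint, adds that the "p-value is used for the final determination". No such rule appears in 8.4.2 or 8.4.3.

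**The concern.** Following the printed code, the treatment p-value left to read off is the one in the coefficient output, which is a Wald test. The global likelihood-ratio test would also cover the two covariates, so it is not a test of treatment. With no events in one arm the penalised likelihood is strongly skewed in the treatment coefficient, and a symmetric Wald approximation is too conservative. The profile interval respects the skew. One table row would then carry an interval and a p-value from two different approximations.

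At stake is a secondary row whose interval lies below 1 while its p-value is above 0.05. The analyst would have to decide, after seeing both, which to believe. The early gallstone endpoints are the likely place, because few events are expected by Month 3 and the endpoint is tabulated for both the site and the external reading.

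**Working it through.** **1. Planning inputs (SAP 4.6, also Protocol 8.3).** "the significance level is 5% for two-sided test, 80% for test power"; placebo: "the incidence of gallstones with placebo was estimated to be 18" per cent; active: "7%, which is the weighted average of the three Ursodiol treatment groups in study 1". The weighted averages reproduce: 136/761 = 17.9% and 12/177 = 6.8%. The sample size reproduces too: (1.96 + 0.842)² × (0.07 × 0.93 + 0.18 × 0.82) / 0.11² = 138.01, then 138/0.8 = 172.5, so 173 per group and 519 in all.

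**2. Wald and profile results, 0 of 138 on active versus k of 138 on placebo.** In the unadjusted two-arm model the Firth estimate equals adding one half to each cell:

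OR = [0.5/138.5] / [(k + 0.5)/(138.5 − k)]

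For k = 6: OR = 0.003610/0.04906 = 0.0736, ln OR = −2.609. With fitted risks 0.5/139 and 6.5/139, the variance is 1/(138 × 0.003597 × 0.9964) + 1/(138 × 0.04676 × 0.9532) = 2.022 + 0.163 = 2.184, so SE = 1.478, z = −1.765 and Wald p = 0.0775. Twice the drop in penalised log-likelihood when the treatment coefficient is fixed at zero is 6.23, so p = 0.0125.

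| Placebo events k | Wald p | Penalised LR p | Profile upper limit |
|---|---|---|---|
| 4 | 0.138 | 0.053 | 1.03 |
| 5 | 0.1017 | 0.0258 | 0.785 |
| 6 | 0.0775 | 0.0125 | 0.633 |
| 7 | 0.0606 | 0.0061 | 0.528 |
| 8 | 0.0484 | 0.0029 | 0.452 |

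The Wald p and the interval disagree at k = 5, 6 and 7 and agree at 4 and 8. The band is the same with 173 per arm. The likelihood-ratio p agrees with the interval in every row.

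**3. With the SAP covariates.** The documents do not give the strata splits, so three were assumed and data sets simulated for 138 and 173 per arm. The conflict arose in 93 to 100% of data sets at 0 v 5 and 0 v 6, in 13 to 33% at 0 v 7 (mean Wald p about 0.047), and in 0 to 5% at 0 v 8. The adjusted band is therefore mostly 5 to 6.

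**4. How often at Month 3.** Assumption: stones accrue evenly. Placebo at Month 3 is then 18%/4 = 4.5%, and active at the planned rate is 7%/4 = 1.75%. Study 1's 600 mg figure, 1.64%, is labelled 6 months, so its Month 3 value is 0.82%. The probability of conflict is P(0 on active) × P(5 to 7 on placebo).

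| | 138 per arm | 173 per arm |
|---|---|---|
| Expected placebo events | 6.2 | 7.8 |
| Expected active events at 7% | 2.4 | 3.0 |
| P(5 to 7 on placebo) | 0.466 | 0.374 |
| Conflict, planned 7% | 0.0875 × 0.466 = 4.1% | 0.0472 × 0.374 = 1.8% |
| Conflict, 1.64% at 6 months | 0.321 × 0.466 = 15% | 0.241 × 0.374 = 9% |

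A constant hazard instead of even accrual gives 3.7% and 1.4% at the planned rate, and 14% and 8% at 1.64%. All of these use the unadjusted band; the narrower adjusted band lowers them.

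**5. The 12-month primary endpoint.** P(0 of 138 at 7%) = 0.93^138 = 0.00004. Expected placebo events are 138 × 0.18 = 24.8. At 0 v 25 the Wald p is 0.004 and the profile upper limit is 0.117, so there is no conflict.

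**The case against.** The strongest reply is that the SAP never prescribes a Wald p-value. The word does not occur; the test is unspecified rather than wrongly specified. That is correct, and the point is stated accordingly. It does not dispose of it, because the SAP specifies this branch down to code and the code as printed supplies no other p-value for treatment.

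A reader might also infer that the p-value overrides the interval at Month 3. The documents do not support this. The sentence making the p-value decisive stands in 8.4.1 for the 12-month primary endpoint. For Month 3 the odds ratio, interval and p-value are only reported, against the general two-sided 0.05 level.

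Nor is the conflict what the plan's rates lead one to expect. At 7% some 2.4 to 3.0 active-arm events are expected by Month 3, not zero. A figure near 25% for 600 mg results only if 1.64% is treated as a 12-month rate, whereas SAP 4.6 labels it 6 months. SAP 4.6 also declines to plan on dose-specific rates.

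The denominator matters as well. The 138 allows for withdrawal over the whole study, while the full analysis set needs only one post-randomisation gallstone assessment, so the Month 3 denominator should lie nearer 173. That favours the lower end of each range. For AST/ALT no rate is given, so no frequency can be attached there. All of this limits the size of the point; none of it removes the mismatch.

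**Conclusion.** The concern holds as a minor specification gap. SAP 11.1 and 15.3 pair a profile-likelihood interval with no matching test, and the default p-value can contradict that interval when one active arm has no events and placebo has 5 to 7 (mostly 5 to 6 after adjustment).

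Under even accrual the chance at Month 3 is about 2 to 4% per dose comparison at the planned rates. It is about 9 to 15% for 600 mg if the Study 1 rate is read as a 6-month rate. Both ranges run from 173 to 138 per arm and are lower with the covariates. They rest on an assumed Month 3 rate and on the inference that the coefficient p-value would be reported. Where the two disagree, the Wald p errs on the conservative side.

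The consequence is confined to secondary and exploratory tables. It does not extend to the primary conclusion: at 12 months a zero arm is very unlikely at the planned rate, and at the expected placebo count interval and p-value agree. Severity is low.

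**What to change.** In SAP 11.1 (Statistical Analysis Methods) and 15.3, state that whenever the Firth fit is used the two-sided treatment p-value comes from the penalised likelihood-ratio test. This compares the Firth log-likelihood maximised with the treatment coefficient free against that maximised with it fixed at zero, covariates retained in both. It is the test that the profile interval inverts, and p and interval agreed for every placebo count checked, from 1 to 15. Report no Wald p-value for that model.

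The cost is one sentence and one extra model fit per zero-cell comparison. Sample size, endpoints and the testing order are unaffected. The sentence should be added before unblinding, so that the test is not chosen after the two answers are seen.

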11.2 Baseline

Unless otherwise specified, the baseline is defined as the last measurement prior to the dose of investigational product without missing data.

11.3 Study Period and Visit Window Definitions

Unless otherwise specified, the point-by-point summary of each assessment variable is presented for the regular visit measurement.

Protocol No.: DW_UDCA005 English Translation Version

Visit	Analysis Label	Actual Point	Visit Window
Visit 1	Screening	- 2 week~ - Day1	
Visit 2	Baseline	Day 1	
Visit 3	3 month	3 month	± 1 week
Visit 4	6 month	6 month	± 1 week
Visit 5	9 month	9 month	± 1 week
Visit 6	12 month	12 month	± 1 week

11.4 Software for Statistical Analysis

All statistical analysis will be performed using SAS® Version 9.4 or higher (SAS institute, Cary, NC, USA).

12. DATA HANDLING COVENTIONS

12.1 Handling of Missing Data

12.1.1 Missing Value of Efficacy Variables

If there is a missing value due to the withdrawal of the subject before the end of the clinical study or a missing a test at a particular point in time, unless otherwise specified, the data is not replaced for analysis but treated as an observed case.

12.1.2 Missing Value of Safety Variables

If there is missing data in analyzing the Safety Set, the analysis is carried out as is without replacing it.

12.2 Repeated or Unscheduled Assessments

For all endpoints, if there is more than one measurement result prior to the first dose of the investigational product, use the baseline value as defined in Section 11.4.

If there is a measurement result on an unscheduled visit after the first dose of the investigational product, on the list of the subject, present it sequentially with the regular visits based on the visit date.

A summary of measurements by time point is presented only for regular visits and not presented separately for unscheduled visits. However, the final result excluding the baseline of the subject that was withdrawn are summarized together with the results of the last visit of the regular visit. In addition, only the results of regular visits are used to test for statistical significance.

12.3 Handling of Incomplete Date

If part of the day or month data is missing from the start or end date of the medical history and

Protocol No.: DW_UDCA005 English Translation Version

prior surgery, concomitant mediation, and adverse events, comparison is made based on the collected data without replacing the dates. However, if all start dates are missing, regard it as starting prior to the first dose of investigational product, and if the end date is missing, regard it as currently being administered.

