6.3.2 Concomitant Medication

Concomitant medication is defined as a drug whose onset of administration is after taking the first dose of the investigational product. If the starting or ending date of the administration is incomplete and it is difficult to distinguish the prior/concomitant medication, it is regarded as concomitant medication. If the start date of the administration is after the end of the clinical study, then it is excluded from the concomitant medication.

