6.5.2 Treatment-Emergent Adverse Events (TEAEs)

The treatment-emergent adverse events (TEAEs) of the adverse events collected during the clinical study are evaluated, and the TEAEs are as follows:

- Adverse events that occurred after the "first dose of the investigational product after randomization"
- Among the symptoms that preceded the "first dose of the investigational product after randomization", adverse events with worsened severity following the "first dose of the investigational product after randomization"

However, if the occurrence date of the adverse event is missing or incomplete and, it is unclear if it had occurred pre or post "dose of the investigational product after randomization", then the event is considered as a TEAE.

[Severity of Adverse Events]

- 1) Mild: Showing symptoms or signs but without hindrance to daily life
- 2) Moderate: The degree to which routine activities are restricted and sufficiently inconvenienced
- 3) Severe: To the extent that daily activities cannot be carried out

[Relevance to Investigational Product]

- 1) Definitely related
- 2) Probably related
- 3) Possibly related
- 4) Probably not related, Unlikely
- 5) Definitely not related, None
- 6) Unknown, Unassessable

Protocol No.: DW_UDCA005 English Translation Version

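### SAP 12.3 and 6.5.2 classify an adverse event with no start date in opposite ways, and SAP 6.3 leaves drugs continued from before the first dose out of the concomitant table

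*Protocol*

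**What the plan says.** **Date rule.** SAP 12.3 (Handling of Incomplete Date) is one pooled rule for medical history, prior surgery, concomitant medication and adverse events. For partly missing dates, "comparison is made based on the collected data without replacing the dates". Where nothing of the start date is known, it says: "if all start dates are missing, regard it as starting prior to the first dose of investigational product". For a missing end date: "if the end date is missing, regard it as currently being administered".

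**Adverse events.** SAP 6.5.2 has its own rule: "if the occurrence date of the adverse event is missing or incomplete and, it is unclear if it had occurred pre or post" the dose, "then the event is considered as a TEAE". It also keeps as TEAEs those symptoms present before treatment that become "adverse events with worsened severity following the" first dose. SAP 6.5.3 defines ADRs within the TEAEs.

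**Drugs.** SAP 6.3.1 makes a drug prior if its onset is before the first dose. SAP 6.3.2 says: "Concomitant medication is defined as a drug whose onset of administration is after taking the first dose of the investigational product". It adds that a drug counts as concomitant when an incomplete start or end date makes it hard to tell the two classes apart.

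**The concern.** An adverse event with no start date is pre-treatment under one section and treatment-emergent under another. Protocol 14.5.1 restricts the summary and analysis of adverse events to TEAEs, so the classification decides whether the event is counted at all. Two programmers could each follow the SAP and report different TEAE, ADR, serious-event or death counts. The 12.3 reading is the one that lowers them.

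The drug definitions raise a second, separate issue. Classifying by onset alone means that the concomitant table does not show everything taken on treatment. These patients are randomised within 2 weeks of gastrectomy (protocol 10.1), so drugs begun around surgery and continued past the first dose are to be expected.

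**Working it through.** There is no figure to reproduce. The check sets the rules side by side and follows one record through to the listed outputs.

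**1. An adverse event with no start date, timing unclear, no worsening recorded**

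| Step | Under SAP 6.5.2 | Under SAP 12.3 |
|---|---|---|
| Onset | Unplaceable | Before the first dose |
| TEAE? | Yes | No |
| Can be an ADR (6.5.3)? | Yes, if related or unassessable | No |
| Overall, SOC/PT and severity tables (9.2.1, 9.2.2) | Counted | Not counted |
| Serious, IP discontinuation and death tables (9.2.3) | Counted if applicable | Not counted |
| Where it appears | TEAE tables and listings | Pre-treatment AE listing (9.2.2) only |

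Every adverse event table named in SAP 9.2.1 to 9.2.3 is restricted to TEAEs or ADRs, so no table picks the event up under 12.3.

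**2. Does 12.3 really reach adverse events?** Yes. Its list of items runs up to "mediation, and adverse events, comparison is made based on the collected data without replacing the dates", and the sentence on wholly missing start dates follows with no exception.

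**3. Can the two be read together?** One could apply 12.3 first, so that an undated event is never unclear. The mention of a missing date in 6.5.2 would then have no effect on a wholly undated event, so this order does not reconcile the text.

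**4. Partial dates.** These do not clash. SAP 12.3 compares the parts that were collected, and 6.5.2 takes whatever remains unplaceable as a TEAE. The conflict is confined to wholly missing start dates.

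**5. A drug with no start date.** SAP 12.3 with 6.3.1 makes it prior. SAP 6.3.2 makes it concomitant if a missing date counts as an incomplete one. Section 12.3 deals with wholly missing dates under a heading about incomplete dates, so that reading is natural, but 6.3.2 does not name missing dates as 6.5.2 does.

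**6. A drug started before the first dose and continued on treatment, with complete dates.** By onset it is prior (6.3.1) and fails the concomitant definition (6.3.2). It therefore enters the prior table and not the concomitant table of SAP 8.3.2. Two other places point the other way:
- Protocol 10.3 says that drugs begun during the gastrectomy admission and continued after discharge are to be collected as concomitant medication.
- SAP 6.3.2 treats an incomplete ending date as a reason why a drug cannot be classified. An ending date can matter only if continued use counts.

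**The case against.** The strongest reply is that 6.5.2 is specific to adverse events and names missing dates, while 12.3 is pooled and ends in wording that fits only drugs. A specific rule normally governs a general one. That is probably what was meant, but the SAP does not say so, and 12.3 names adverse events expressly. The reply shows which way to repair the text; it does not show that repair is unnecessary.

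The affected set may also be close to empty. Adverse events are collected at Visits 3 to 6, onset date is a required item (protocol 11.2.11 and 15.2.3), and data issues are resolved by clarification form before lock (protocol 10.5.2). This stands and limits the size of the point.

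A reader might infer that undated events disappear from all safety output. They do not. They stay in the pre-treatment listing, they remain TEAEs if worsening was recorded, withdrawals and their reasons still appear in the disposition output (SAP 7.1), and expedited reporting of serious events (protocol 15.2.4) is separate from these tables.

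A reader might also infer that the drug definition undermines per-protocol decisions. No section ties the concomitant table to them. Exclusions rest on significant deviations documented before unblinding (protocol 13.4 and 14.1.1) and are shown in separate outputs (SAP 7.2 and 7.3). Nor does a carried-over drug vanish, since it is in the prior table. The documents give no basis for saying what share of drug use is affected, and protocol 10.3 exempts many in-hospital drugs from collection.

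**Conclusion.** The contradiction between SAP 12.3 and 6.5.2 is real for adverse events with a wholly missing start date and no recorded worsening. Following 12.3 removes them from every adverse event table, and that direction is anti-conservative. The documents give no count of such events. The number is probably small, so no percentage should be attached; but any one of them could be serious or fatal, and the repair is cheap.

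The missing-date conflict for drugs holds only on the natural reading that incomplete includes missing, and its effect is a move between two descriptive tables. The onset-only drug definition does not depend on missing dates. It applies to every drug started before the first dose and continued, and it conflicts with protocol 10.3 and with the wording of 6.3.2 itself. Some of this may be loose translation, but the text as it stands would be programmed that way. Neither issue touches the primary efficacy analysis.

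**What to change.** - **SAP 12.3:** limit the sentence that places a wholly missing start date before the first dose to medical history and prior surgery.
- **Adverse events:** state in 12.3 that 6.5.2 governs. An event is a TEAE unless the available partial start date or the end date shows that onset was before the first dose, without later worsening.
- **Drugs, dates:** state in 12.3 that 6.3.2 governs, and extend 6.3.2 to missing as well as incomplete dates.
- **Drugs, definition:** define concomitant medication as any drug taken on or after the first dose, including those started earlier and still ongoing.

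The cost is a few sentences in the SAP and the matching derivation code. Design, data collection and the primary analysis are unchanged. The changes should be made before unblinding.
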